4. TRIAL POPULATION

4.1. Number of Patients

It is anticipated that any patient participating in a setmelanotide clinical trial could be a candidate for enrollment in this extension trial. Based on the number of patients currently enrolled or planned for enrolment in setmelanotide clinical trials, it is anticipated that up to 500 patients may be enrolled in this trial; however, expansion in enrollment may occur if additional patients with obesity due to monogenic, syndromic or acquired disorders affecting the MC4R pathway are enrolled in Phase 2 or Phase 3 clinical trials evaluating setmelanotide. It is anticipated that up to 100 centers located worldwide will participate in this trial. In the event additional patients are to be enrolled, additional sites may be added, as necessary.

4.2. Patient Selection Criteria

The specific inclusion and exclusion criteria for enrolling patients in this trial are presented in the section below. As these patients are ultra-rare, any criteria not fulfilled will be reviewed with the sponsor. Assuming no severe health concerns, a joint determination will be made regarding the acceptability of enrolling patients not fulfilling all criteria on a case-by-case basis. Any exceptions to the inclusion and exclusion criteria will be documented in writing and approved by responsible sponsor medical personnel prior to dosing the patient.

4.2.1. Inclusion Criteria

- 1. Patients aged 2 or older (or aged >2 years as per local regulations; ; only patients aged 12 years or older may be enrolled in the trial in Greece; only patients 6 years or older may be enrolled in the trial in Germany) who have completed participation in a previous setmelanotide clinical trial.
- 2. If patient received setmelanotide on an open-label basis in a previous setmelanotide clinical trial, patient demonstrated adequate safety and meaningful clinical benefit (efficacy) in the previous setmelanotide trial. Meaningful clinical benefit is defined as follows:
 - Patients 18 years of age or younger that have completed participation on active drug and demonstrated adequate safety and at least 3% BMI reduction or reduction in BMI Z-score of 0.2 compared to baseline.
 - Patients over 18 years of age should show reduction of 3% BMI compared to baseline.

If the patient participated in a double-blind basis in the previous placebo-controlled clinical trial, patient tolerated blinded study drug.

- 3. Patient and/or parent or guardian is able to communicate well with the investigator, to understand and comply with the requirements of the trial, and to understand and sign the written informed consent/assent. The patient must consent/assent to participate in the trial.
- 4. Patient must meet one of the following requirements regarding contraception:
 - If a female of childbearing potential, defined as fertile, following menarche and until becoming post-menopausal unless permanently sterile (hysterectomy, bilateral salpingectomy, or bilateral oophorectomy), must use a highly effective form of contraception as outlined in Section 6.2.1.
 - If a female of non-childbearing potential, defined as permanently sterile (status post hysterectomy, bilateral oophorectomy, or bilateral salpingectomy) or postmenopausal for at least 12 months (and confirmed with a screening folliclestimulating hormone (FSH) level in the post-menopausal laboratory range), contraception is not required during the trial.
 - Younger female patients who have not reached menarche upon trial entry will be assessed for Tanner staging and at first menarche will be required to comply with contraception requirements and pregnancy testing as outlined in the protocol.
 - If a male with female partner(s) of childbearing potential, must agree to a double barrier method if they become sexually active during the trial. Furthermore, male patients must not donate sperm during and for 90 days following their participation in the trial.

4.2.2. Exclusion Criteria

- 1. Pregnant and/or breastfeeding women.
- 2. Significant dermatologic findings relating to melanoma or pre-melanoma skin lesions (excluding non-invasive basal or squamous cell lesion), determined as part of a screening comprehensive skin evaluation performed by a qualified dermatologist. Any concerning lesions identified during the screening period will be biopsied and results known to be benign prior to enrollment. If the pre-treatment biopsy results are of concern, the patient may need to be excluded from the trial.
- 3. Patient is, in the opinion of the investigator, not suitable to participate in the trial.
- 4. Current, clinically significant disease, if severe enough to interfere with the trial and/or would confound the results. Any such patients should be discussed with the sponsor prior to enrollment in the trial.
- 5. Diagnosis of schizophrenia, bipolar disorder, personality disorder or other Diagnostic and Statistical Manual of Mental Disorders (DSM-III) disorders that the investigator believes will interfere significantly with trial compliance.
- 6. A Patient Health Questionnaire-9 (PHQ-9) score of ≥ 15 .
- 7. Any suicidal ideation of type 4 or 5 on the C-SSRS. Any lifetime history of a suicide attempt, or any suicidal behavior since the last visit in the index trial.

Note: Patients who are unable to complete the C-SSRS due to significant neurocognitive defects may be enrolled in the trial, as long as in the opinion of the investigator there are no clinical signs or symptoms of suicidal behavior.

- 8. History of significant liver disease or liver injury, or a current liver assessment due to abnormal liver tests (as indicated by abnormal liver function tests, alanine transaminase [ALT], aspartate transaminase [AST], alkaline phosphatase, or serum bilirubin >1.5× the upper limit of normal [ULN] for any of these tests) for an etiology other than non-alcoholic fatty liver disease (NAFLD). Thus, any underlying etiology besides NAFLD, including diagnosed non-alcoholic steatohepatitis (NASH), other causes of hepatitis, or history of hepatic cirrhosis is exclusionary, but the presence of NAFLD is not exclusionary.
- Severe renal dysfunction defined by a glomerular filtration rate (GFR)
 <30 mL/min/1.73 m² in patients <12 years of age or end stage renal disease (GFR
 <15 mL min/1.73 m² (see Appendix 11.4 for GFR calculation).
- 10. History or close family history (parents or siblings) of skin cancer or melanoma (not including non-invasive/infiltrative basal or squamous cell lesion), or patient history of ocular-cutaneous albinism.

4.3. Patient Identification and Registration

Patients who complete treatment in a previous trial of setmelanotide (i.e., index trial) and wish to continue with setmelanotide treatment will be considered for eligibility to enter this extension trial. Patients who are candidates for enrollment into the trial will be evaluated for eligibility by

the investigator to ensure that the inclusion and exclusion criteria have been satisfied and that the patient is eligible for participation in this clinical trial.

All patients enrolled in the trial will be assigned a unique 9-digit number which will be a combination of the last 2-digits of the current protocol number (RM-493-022), the last 2-digits of the index protocol number (RM-493-XXX), the 2-digit site number, and a sequential 3-digit patient number, which will be used to identify patients throughout their participation in the trial. Patient numbers will be assigned sequentially starting at 001 (i.e., the first patient enrolled from index Protocol RM-493-012 at Site 10 would be assigned Number 22-12-10-001). Once a patient number has been assigned, it cannot be reused.

Note that patient numbers may be modified to identify those patients who transition from this extension trial into another setmelanotide clinical trial and, as applicable, transition back into the extension trial. However, the patient number will enable tracking the patient across both clinical trials.

All patients withdrawn prior to completing the treatment period should be strongly encouraged to complete the ET visit as outlined in the Schedule of Assessments (SOA) (Table 1 in Section 6), even if they are no longer receiving study drug. (Refer to Section 3.4 for information regarding completion of the Termination Visit for patients who transition into another setmelanotide clinical trial.)

In case of discontinuation, all AEs should be followed as described in Section 7.4; any skin AEs should continue to be followed, if at all feasible, for up to ~90 days to confirm near, or complete resolution (as has been shown in previous trials).

The sponsor will provide support for patient and caregiver travel, will make available visiting home health care professionals, and other necessary logistical support to ease the burden on the patient and to facilitate compliance with the trial procedures.

4.5. Patients' Re-entry from Other Trials

Patients that have left the current trial to enter other setmelanotide trials might re-enter the current trial upon discussion with the sponsor.

If a patient decides to withdraw consent from another setmelanotide trial, they might not be able to re-enter the current trial unless the reason for ET was due to a tolerability issue with a different setmelanotide formulation. All the other circumstances will be discussed with the sponsor on a case-by-case basis and supporting documentation justifying re-entry should be provided by the investigator.

5. TRIAL TREATMENTS

5.1. Study Drugs

All study drugs are for investigational use only and are to be used only within the context of this protocol. Setmelanotide will be supplied by the sponsor.

Setmelanotide is a clear, colorless to slightly opalescent solution essentially free of visible particulates. Setmelanotide will be administered as a subcutaneous (SC) injection once daily.

All unopened study drug must be kept in a secure, limited-access storage area at a temperature between 2°C to 8°C. Setmelanotide is stable at room temperature for a short time period that will allow patients to transport study drug home; ice packs and cooler bags will be provided for patients and caregivers who will travel long distances from the clinic. Patients will be encouraged to proceed directly home after clinic visits in which study drug is dispensed in order to minimize the amount of time the study drug is exposed to potentially elevated temperatures. Once at home, the unopened study drug must be stored in the patient's refrigerator. Opened study drug may be stored at room temperature for up to 30 days.

A separate pharmacy manual with specific instructions for the management of study drug will be provided to the investigative site.

5.2. Study Drug Dose and Administration and Dose Adjustments

Study Drug Dose at Trial Entry: Patients who received setmelanotide on an open-label basis in the index trial will begin this extension trial on the same dose of setmelanotide they were taking when they completed their index trial, unless tolerability or safety reasons justify a dose decrease. Patients who received double-blind study drug in a placebo-controlled index trial will start open-label setmelanotide in this trial with the starting dose from the index trial. The dose titration should follow the scheme in the index trial and in consultation with the sponsor.

Study Drug Administration: Trial patients will receive open-label setmelanotide by SC injection once daily (administered in the morning). Patients and/or their caregivers (including home health practitioners) will be responsible for all procedures associated with study drug administration at all times, i.e., drawing up, and self-administering the study drug once daily. Patients should be

instructed to rotate injection sites as per the dosing instructions and to avoid tight fitting clothing near the injection site to potentially reduce any injection site reactions.

Study drug is administered by patients/caregivers beginning the morning of Day 1 and for the duration of dosing. (If the index study drug is administered on the last day of the index trial/Day 1 of the current trial, then study drug administration in the current trial will begin on Day 2.) Patients/caregivers will draw up and self-administer/administer the drug once on a daily basis in the morning. On days with clinic visits, the patients/caregivers will administer the drug in the clinic in the presence of the clinical staff to ensure proper technique. Patients/caregivers will return all used vials to the clinic when they visit (the number recorded) and both clinic administration of study drug, as well as outpatient study drug administration will be recorded in a trial diary.

Study Drug Administration in Patients with Severe Renal Impairment

In Patients ≥ 12 years of age with severe renal impairment (eGFR 15 to 29 mL min/1.73 m²), the starting dose of setmelanotide is 0.5 mg (0.5 mL) injected subcutaneously QD for 2 weeks. The dose may be increased by 0.5 mg QD every 2 weeks, if tolerated, to a maximum of 1.5 mg QD. If the starting dose is not tolerated, treatment should be discontinued.

The use of setmelanotide in patients <12 years of age with severe renal impairment is not permitted in this trial.

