5.2.1. Dose Adjustments

The patient will continue the same dose of setmelanotide as taken at the end of the index trial. However, dose changes may be considered for safety/tolerability or efficacy reasons after discussion with the sponsor. For patients entering from a double-blind index trial, the starting dose will be the initial dose from the index trial. Dosing steps will also mirror the titration scheme from the index trial. During the course of the trial, if the patient attains a BMI or BMI Zscore within the normal range, per local guidelines, the investigator can reduce the dose of setmelanotide to the appropriate dose level, in order to maintain normal BMI or BMI Z-score and appetite, at their discretion. This should be discussed with the sponsor prior to initiating dose reduction.

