6. TRIAL ASSESSMENTS

6.1. Overview of Schedule of Assessments

The SOA to be conducted is depicted in Table 1.

Any patient withdrawing from the trial will complete the ET visit, if possible.

Discussion of this trial with the patient should occur prior to completion of their index trial and attempts should be made to minimize gaps/discontinuation of setmelanotide during transition from their index trial to this extension trial. Visit 1 of this trial will coincide with the final visit from the index trial, if possible. Visit procedures from the last visit of the index trial and the first visit of the extension trial are not intended to be duplicated. Thus, any repeat assessments do not need to be conducted and data from the last visit of the index trial will be used as V1 data in this trial as applicable. Patients will begin this extension trial on the same dose of setmelanotide that they were taking when they completed their index trial.

In order to provide flexibility to the patient and trial staff for the number of clinic visits, the actual scheduling of clinic visits can allow flexibility in timing of visits.

The actual scheduling and timing of clinic visits is flexible to accommodate the patient and trial staff. The SOA depicts the weeks visits are to be scheduled and in some cases, multiple visits are to be scheduled within a range of weeks.

The investigators will adhere to the site-specific blood volume limits for safety laboratory and

analyses to ensure minimal distress to the pediatric patients (Appendix 11.5). Due to the age of the children, it may not be possible to collect blood samples for all laboratory tests at every trial visit. After enrollment, if blood sample collection for all laboratory tests is not possible, then the samples should be collected in the following descending order of priority:

- 1. safety laboratory tests,
- 2. anti-setmelanotide antibodies (ADA),
- 3.
- 4. glycated hemoglobin (HbA1c),
- 5. ,
- 6.
- 7. laboratory assessments indicative of nutritional status (e.g., albumin).

If it is not possible to collect the safety laboratory samples on 2 consecutive visits, the patient should be discussed with the sponsor. Refer to the Laboratory Manual for the volumes of blood to be collected.

Protocol

Trial Period								pen-lab e Treat									ET ²	Follow Up ²⁶
Visit Number	V1	V2- V4	V5	V6- V8	V9	V10- V12	V13	V14- V16	V17	V18- V20	V21	V22- V24	V25	V26- V28	V29 (EOT)	Trans- ition		

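### The protocol gives patients aged 12 or older with severe renal impairment two entry-dose rules, and its visible text does not say how they relate

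*Protocol*

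**What the plan says.** **Eligibility.** Exclusion 9 (synopsis and Protocol 4.2.2) bars a GFR below 30 only under age 12, and a GFR below 15 at any age. A patient aged 12 or older with a GFR of 15 to 29 can therefore enrol. Section 5.2 adds that children under 12 with severe impairment may not be treated, so they fall outside this point.

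**Renal paragraph.** Protocol 5.2, under its own sub-heading, addresses patients "≥ 12 years of age with severe renal impairment" (eGFR 15 to 29). For them "the starting dose of setmelanotide is 0.5 mg (0.5 mL) injected subcutaneously QD for 2 weeks". The dose may rise by 0.5 mg every 2 weeks if tolerated, "to a maximum of 1.5 mg QD". If the first dose is not tolerated, treatment stops.

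**General rule after an open-label index trial.** Under Section 5.2 these patients "will begin this extension trial on the same dose of setmelanotide they were taking when they completed their index trial". That sentence carries one exception: "unless tolerability or safety reasons justify a dose decrease". Section 3.2 has the same rule and exception, and adds a second exception where more clinical effect is wanted. Section 5.2.1 says: "The patient will continue the same dose of setmelanotide as taken at the end of the index trial". Its next sentence lets changes for safety, tolerability or efficacy be considered once discussed with the sponsor. Section 6.1 says "Patients will begin this extension trial on the same dose of setmelanotide that they were taking when they completed their index trial", with no exception, and the Trial Design text of the synopsis says the same. The study drug row of the synopsis sends doses and titration to the index-trial scheme and cites Section 5.2.

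**General rule after a double-blind index trial.** These patients "will start open-label setmelanotide in this trial with the starting dose from the index trial" (Section 5.2; the synopsis, Section 3.2 and Section 5.2.1 agree), with titration as in the index trial.

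**The concern.** The eligibility rule and the renal paragraph together identify a group of patients to whom both dosing rules apply by their terms. One rule takes the dose from the index trial. The other sets a fixed start, step and ceiling. Neither mentions the other, and the exceptions attached to the general rule call for a judgement and do not name renal function.

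A site could follow one passage and depart from another on a matter of dosing safety. Two sites could treat the same kind of patient differently and each cite the protocol. The summaries would probably not show it: the SAP pools safety data across index studies (3.5), defines no subpopulations (3.8), and in the visible text of 4.5.1 reports exposure as duration rather than dose.

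**Working it through.** There is no planned figure to reproduce: Protocol 8.1 sets aside sample size and power. The check is a comparison of passages, with a small illustration from the protocol's own doses.

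**Step 1. The rules side by side, for a patient aged 12 or older with eGFR 15 to 29.**

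| Situation | General rule | Renal paragraph of 5.2 |
|---|---|---|
| Enters from an open-label index trial | Final index-trial dose; a decrease for safety or tolerability is possible under 3.2, 5.2 and 5.2.1, but the synopsis design text and 6.1 give no exception | 0.5 mg, steps of 0.5 mg, maximum 1.5 mg; not stated whether it covers a patient already on drug |
| Enters from a double-blind index trial | Index trial's starting dose and titration | Same schedule; not stated whether it replaces the index scheme |
| eGFR falls to 15–29 during the trial | Current dose; changes may be considered after sponsor discussion (5.2.1) | Not stated whether it then applies |

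**Step 2. What the renal wording can mean for a patient already on drug.** The reference to a starting dose, and the consequence if that dose is not tolerated, point to patients beginning treatment. The population, defined only by age and renal function, and the stated maximum point to every such patient. Three readings are open: continue the index dose, continue but capped at the maximum, or restart at the renal starting dose. The visible text does not choose among them.

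**Step 3. Illustration only.** Suppose such a patient finished an open-label index trial at the 3 mg target dose (Section 3.2.1).

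- Entry dose: 3 mg under the general rule, 0.5 mg under the renal paragraph; 3 / 0.5 = 6-fold.
- Ceiling: 3 mg against 1.5 mg; 3 / 1.5 = 2-fold.
- Earliest time to 1.5 mg under the renal schedule: (1.5 − 0.5) / 0.5 = 2 steps of 2 weeks = 4 weeks.
- Carried-over dose of 1.0 or 1.5 mg: the ceiling is respected, but entry doses still differ (1.0 / 0.5 = 2-fold; 1.5 / 0.5 = 3-fold).
- The entry doses agree only when the general rule also yields 0.5 mg.

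**Step 4. Renal decline during follow-up.** Participation lasts up to 7 years (5.4), and creatinine is in the safety panel drawn at each visit (Table 1, footnote 14), so a fall into the 15–29 range would be seen. Section 1.1.1 states what happens to the 4 and 5 mg doses when body weight falls to a threshold. No visible passage does the same for renal function.

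**The case against.** The best reply is that this is a general rule followed by a specific exception in the same section, and that a specific paragraph governs its own population. A renal maximum written into the protocol is also an obvious safety reason under the exception in Section 5.2. Section 5.2.1 allows safety changes after sponsor discussion, and exclusion 4 sends patients with significant interfering disease to the sponsor before enrolment. Section 6.1 and the synopsis can be read as summaries of 5.2, and the synopsis drug row cites that section.

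This is a reasonable reading, and many sites would adopt it. But the protocol does not state it, and it leaves open whether a patient on a higher dose restarts, is capped or continues. The exceptions are discretionary, whereas the renal schedule is fixed.

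Two further replies limit the point. First, the public Section 5.2.1 looks incomplete: Section 3.2.1 refers to it for escalation up to 5 mg, yet no escalation text is visible there, while footnote 10 of SAP Table 1-2 has such text. A reconciling sentence may exist in redacted text, so the gap is established only for what can be read. Second, the index protocols are not available. If they already used the same renal schedule, patients would arrive at or below 1.5 mg and the conflict over the maximum would disappear. A patient arriving above 0.5 mg would still face two entry doses.

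**Conclusion.** The inconsistency is real in the visible text and should be corrected, because it concerns dosing safety and needs only wording. It is confined to patients aged 12 or older with eGFR 15 to 29, who are probably few.

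A reader might infer three stronger things that the documents do not support.

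- *That this is the usual case because nearly all entrants are already on drug.* No passage says so, and the protocol provides for entrants from double-blind trials. SAP Table 1-1 counts 9 + 13 + 119 + 12 + 38 + 14 + 1 = 206 participants by index study, but not by renal function.
- *That doses will differ 6-fold in practice.* That figure assumes a patient with eGFR 15 to 29 who finished on 3 mg. The documents do not show that any such patient exists.
- *That one of the two rules is clinically wrong.* The documents show that the rules are not reconciled, not which one is right, and no view is taken on that here.

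The conclusion assumes that any redacted part of Section 5.2.1 does not already settle the relation between the rules.

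**What to change.** Reconcile the renal paragraph of Protocol 5.2 with the general dosing text in 5.2, 5.2.1, 3.2, 6.1 and the synopsis (Trial Design and study drug rows). The revised text should:

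1. Say whether the renal paragraph covers each of three groups: patients rolling over on drug, patients entering from blinded treatment, and patients whose eGFR falls to 15–29 during the trial.
2. State which passage prevails where both apply.
3. Add a cross-reference to the renal paragraph wherever the same-dose rule is repeated.

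The dose rule itself is a matter for the sponsor's clinical team. If redacted text in 5.2.1 already settles the relation, only the cross-references are needed. The cost is protocol wording, plus the ethics and regulatory steps that Section 9.5 requires for any modification. Sample size and planned analyses are unaffected.
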